As understanding of the cause of Dentin Hypersensitivity, the most appropriate treatment would be occlusion and blockage of exposed dentinal tubules and inhibition of the movement of intratubular fluid and the agents which have ability to seal and occlude the dentinal tubules are ideal for the treatment of Dentin Hypersensitivity^{17, 18}. Based on the mechanism of action, different agents have been widely used all around the world for the treatment of Dentine Hypersensitivity. Potassium nitrate used as a Nerve desensitizing agent and is widely used in dentifrices. Gluteraldehyde, Silver nitrate, Zinc chloride, Strontium chloride hexahydrate used as Protein precipitating agents and used in the treatment of Dentine Hypersensitivity by occluding patent tubules. Sodium fluoride, Stannous fluoride, Strontium chloride, Calcium phosphate, Calcium carbonate, Bio active glasses used as dentinal tubules Plugging agents. Fluoride varnishes, Oxalic acid and resin, Glass ionomer cements, Composites, Dentin bonding agents used as Dentine adhesive sealers. Lasers such as Neodymium:yttrium aluminum garnet (Nd-YAG) laser, GaAlAs (gallium-aluminium-arsenide laser), Erbium-YAG laser nowadays also used for the treatment of Dentin Hypersensitivity. Researches have been taking place on several other

materials among which Propolis is of special interest which has been used in homeopathic and herbal practices since long time ^{19,20}.

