1.6 Null Hypothesis

[figure not shown]
There is no difference in the efficacy of Propolis and Dentine Bonding Agent in the treatment of Dentin Hypersensitivity

1.7 Operational Definitions:

Dentine Hypersensitivity: Painful condition that arises from exposed vital dentine due to external stimulation of exposed dentinal tubules. ^{1,2}

Scaling and root debridement [SRD]: Scaling refers to the removal of plaque and calculus from the tooth surface whereas debridement is the removal of the necrotic cementum from the root surface.

Visual Analog Scale [VAS]: A Visual Analogue Scale (VAS) is a measurement instrument for subjective characteristics or attitudes that cannot be directly measured. This psychometric response scale is frequently used in epidemiologic and clinical research to measure the intensity or frequency of various symptoms.

Schiff cold air sensitivity scale⁴⁹: This scale is mainly used to evaluate subject response to a stimulus like air or evaporative. This scale is scored as follows:

1. Subject does not respond to air stimulus.
2. Subject responds to air stimulus but does not request discontinuation of stimulus.
3. Subject responds to air stimulus and requests discontinuation or moves from stimulus.
4. Subject responds to air stimulus, considers stimulus to be painful, and requests discontinuation of the stimulus.

CHAPTER 2: METHODOLOGY

2.1 Study Design:

A Single blinded Randomized Clinical Trial.

2.2 Study Setting:

This singled- centered Study will be conducted in Periodontology Department of Dow International Dental College (DIDC) of Dow University of Health Sciences (DUHS).

2.3 Study Duration:

Study will be conducted in six months after approval of the synopsis

2.4 Study Population:

2.4.1 Inclusion Criteria:

1. Subjects included in this study will be selected from outpatients attending the periodontology department of DIDC for the problem of Dentin Hypersensitivity.
2. Healthy males or females of 20- 45 years of age and will have at least 2 vital teeth with hypersensitivity on facial surfaces to evaporative stimulus.
3. Patients with Miller's Class I and II gingival recession will be included.
4. Patients with Score I of Silness and Loe Plaque Index⁵⁰.
5. The patients should have no systemic and mental illness.
6. Patients who used Flouride dentifrices for hypersensitivity but could not get relief from it.

2.4.2 Exclusion Criteria:

[figure not shown]

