1. Patients with Carious, Cracked or Restored teeth, Abutment teeth used of Removable or Fixed Prosthesis and tooth with any other dental pathology.
2. Patients using analgesics, mood alteration drugs during last six months.
3. Smoker, pregnant and nursing mothers.
4. Patients using tooth whitening or bleaching agents in the last six months,
5. Patients undergoing orthodontic therapy and history of periodontal surgery during last six months.
6. Patients who refuse to give consent.
7. Patients who had Score 2 and 3 of Calculus index will also be excluded from this study.

2.5 Sample Size:

Total 50 patients will be carried out (25 in each group). Using PASS version 11, test for Pair means with 99% Confidence Interval and Power of test, mean difference of degree of sensitivity 1.8 (1.9 – 0.01) ²⁷ and 0.42 of Standard Deviation difference (3.35 – 2.93) ²⁷, sample size is 5 patients per group which we have increased to 25 patients per group.

2.6 Sampling Technique:

Diagnosis of Dentine Hypersensitivity will be made by obtaining detailed dental history and clinical examination of the patients prior to include in the study. History and clinical examination will eliminate and exclude the other forms and causes of Dentine Hypersensitivity which will not meet the inclusion criteria of this study. Definitive diagnosis of Dentine Hypersensitivity will be made by using Evaporative or Air blast stimulus from triple dental syringe on the sensitive surface. Then participants will be allocated to two groups through sealed envelope method. Groups will be named as Group A (Propolis) and Group B (Dentine Bonding Agent). It will only be disclosed out at the time of application of desensitizing agents by Operator.

2.7 Data Collection Procedure:

After explanation of the procedure, efficacy and safety of the materials used, possibilities of receiving either treatment options that is Propolis or Dentine Bonding Agent, the patients will be asked to sign a consent form at first (Appendix I & II). After the consent, a complete history will be obtained from the patient regarding his systemic health, medications, dental treatment and hygiene habits and smoking (Appendix III).

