Only the Principal Investigator will be blind to the intervention given to the participants. Application of desensitizing agents to participants will be carried out by trained and experienced operator and it will only be disclosed to operator at the time of application. Operator will inform the participant about the intervention before applying and patients will not be blinded. Desensitizing agents will be applied on day 0 (baseline). Complete isolation of proximal sides from hypersensitive teeth will be done by using cotton rolls. Hypersensitive teeth surfaces will be dried by cotton pellets. Propolis will then be applied by brush on sensitive surfaces and left undisturbed for 60 seconds to let it dry. Application of Dentine Bonding Agent on sensitive surfaces will be applied single coated for 20 seconds, gently apply air for 5 seconds and cure for 10 seconds (as manufacturer's instructions). For Score 4-6 s(Moderate Pain) & 7-10 (Severe Pain) on VAS and grade 3 (Subject responds to air stimulus, considers stimulus to be painful and requests discontinuation of stimulus) of Schiff Cold Air Sensitivity Scale, application of Propolis

and Dentine Bonding Agent will be applied under Local Anesthesia and response will be recorded on next day.

Care should be taken to ensure that none of the products will touch other areas of oral mucosa. Patients will be instructed not to rinse, drink or eat for half an hour after the application of treatment agents and avoid using any desensitizing dentifrices during the course of investigation.

The clinical evaluation of Dentin Hypersensitivity will be done before and after the application of Desensitizing agents at baseline (Day 0), and also on day of re-assessment at 7th, 15th and 30th day (Appendix III).

2.8 Data Analysis:

2.8.1 Study Variables:

Independent Variables:

- Sessions (Days)
- Groups

Dependent Variables:

- Visual Analog Scale (VAS)
- Schiff Cold Air Sensitivity Scale

2.8.2 Statistical Analyses:

Statistical Package for Social Sciences (SPSS) version 20 will be used to analyze the data. The level of statically significance will be set at $p < 0.05$. to see the comparison within groups, Friedman test will be applied. For Pairwise comparison, Wilcoxon Signed Ranked Test will be used. For between groups comparison, Mann- Whitney U- Test will be applied.

2.9 Ethical considerations:

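### Eligibility sets no look-back for earlier desensitizing toothpaste or in-office desensitization, so some Day 0 scores may be on-treatment scores

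*Combined protocol and SAP*

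**What the plan says.** The only restriction on desensitizing toothpaste is in section 2.7, among the instructions that follow application of the study agent: patients are to "avoid using any desensitizing dentifrices during the course of investigation". The same section places debridement, the pretreatment score and the application all on Day 0. It issues every patient the same standard toothpaste and describes no run-in.

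Section 2.4.2 does look back for other exposures:
- "Patients using analgesics, mood alteration drugs during last six months"
- "Patients using tooth whitening or bleaching agents in the last six months"
- "Patients undergoing orthodontic therapy and history of periodontal surgery during last six months" (the six months attaches most naturally to the surgery, since orthodontic therapy is described as current)

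The nearest it comes to earlier in-office treatment is "Patients with Carious, Cracked or Restored teeth, Abutment teeth used of Removable or Fixed Prosthesis and tooth with any other dental pathology".

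Inclusion criterion 6 in section 2.4.1 brings in "Patients who used Flouride dentifrices for hypersensitivity but could not get relief from it", with no stop date. Section 2.7 also says that "a complete history will be obtained from the patient regarding his systemic health, medications, dental treatment and hygiene habits and smoking", but no eligibility rule refers to prior desensitizing treatment. Section 1.1 states "Potassium nitrate used as a Nerve desensitizing agent and is widely used in dentifrices" and lists fluoride varnishes, oxalates, dentin bonding agents and lasers among treatments in use.

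**The concern.** The trial recruits outpatients who attend for hypersensitivity and have already tried to treat it. The plan's own background makes prior exposure to potassium pastes and in-office agents foreseeable. By barring desensitizing paste during the study, the plan accepts that it can affect the outcome. By looking back for bleaching and analgesics, it accepts that earlier exposures can carry over. The exposure closest to the outcome has no look-back.

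Two kinds of patient can therefore enter. One uses a desensitizing paste up to Day 0 and stops on the day the study agent is applied: the baseline is lowered, and the later scores contain the loss of the paste's effect. The other had a varnish, laser or bonding coat weeks before and enters with tubules that may be partly sealed. This patient could even have received an agent of Group B's own class.

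In both cases the change from Day 0 to Days 7, 15 and 30 no longer reflects the study agent alone.

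**Working it through.** **The plan's own figure.** Section 2.5 gives 5 per group from a paired-means calculation, raised to 25. Reading it as two-sided alpha 0.01 and power 0.99, with difference 1.8 and SD 0.42, a paired t calculation gives n = 5 (power 0.995; n = 4 gives 0.893). The figure reproduces, but it does not bear on eligibility.

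**Reading the rules together.**

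| Exposure before Day 0 | Rule in 2.4.2 |
|---|---|
| Analgesics, mood drugs | excluded, six months |
| Whitening or bleaching | excluded, six months |
| Periodontal surgery | excluded, six months |
| Restored teeth (would cover composite or glass-ionomer restorations) | excluded |
| Varnish, oxalate, bonding coat, laser | not named |
| Desensitizing dentifrice | not named; barred only during the investigation (2.7) |

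**Possible size.** The documents give neither the share of prior users nor a residual effect, so both are assumed. Let q be the share who stop an acting product on Day 0, and w the VAS points they lose by follow-up.

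- Understatement of mean improvement within each arm = q × w.
- Chance between-arm shift, 25 per arm: mean 0 and SD = w × √(2q(1−q)/25).

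| q | w | Within-arm understatement | SD of chance between-arm shift |
|---|---|---|---|
| 0.25 | 0.5 | 0.13 | 0.06 |
| 0.30 | 1 | 0.30 | 0.13 |
| 0.30 | 2 | 0.60 | 0.26 |
| 0.50 | 1 | 0.50 | 0.14 |
| 0.50 | 2 | 1.00 | 0.28 |

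**Chance imbalance.** With q = 0.30 there are 15 users among 50. The hypergeometric probability of a split at least as uneven as 10 v 5 is 0.217 counting both directions, or 0.108 against a given arm. A 10 v 5 split shifts the contrast by (10 − 5)/25 × (1 to 2) = 0.2 to 0.4 points.

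**Putting that in proportion.** Section 2.5 quotes SDs of 2.93 and 3.35. Assuming VAS-like units, the between-arm standard error is √(2/25) × 2.93 = 0.83 to √(2/25) × 3.35 = 0.95. The shift is then 0.2/0.95 = 0.2 to 0.4/0.83 = 0.5 standard errors. Prior use adds variance q(1−q)w² = 0.21 × 1 = 0.21 to 0.21 × 4 = 0.84. Against 3.35² = 11.22 and 2.93² = 8.58, that is 0.21/11.22 = 2% to 0.84/8.58 = 10%.

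**The case against.** The strongest reply is that the objective and null hypothesis concern the comparison between groups. Prior treatment precedes allocation, so its expected effect on that comparison is zero, and a valid randomized test already allows for chance imbalance. This stands. A reader might infer from the missing look-back that the Mann-Whitney result is biased towards one agent. The documents do not support that, unless residual product interacts with one agent, and nothing in them shows it does.

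The within-group contrast is also weak for other reasons. There is no untreated arm, and scaling, a new toothpaste and dietary counselling all fall on Day 0. That stands too, but these are applied to every patient and described in the plan, whereas prior desensitization is neither controlled nor reported.

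Existing rules remove some cases. Restored teeth are excluded. Entry needs at least two vital teeth that respond to an evaporative stimulus (2.4.1), confirmed by air blast (2.6), so a fully sealed tooth would not qualify. It would therefore be too strong to say that earlier professional treatment is not excluded at all. However, no minimum score is set, so a partly sealed tooth can still enter.

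Inclusion criterion 6 requires that fluoride paste gave no relief, which makes a residual effect of that product less likely. It does not cover potassium pastes or in-office agents, and lack of relief is not a washout.

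Finally, the history form cited as Appendix III is not in the text available to me, so I cannot say what it records. The eligibility list still attaches no rule to prior desensitization.

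**Conclusion.** The gap is real and its likely effect modest. Followed as written, the plan can enrol patients whose Day 0 score is an on-treatment score. The consequence falls mainly on the within-group Friedman and Wilcoxon changes, which can mix the study agent with withdrawal or persistence of an earlier one. Randomization does not remove this, because it affects both arms. The between-group test gains noise and possible chance imbalance; section 2.8.2 states no adjustment for prior use.

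The size is unknown. The 30% share and the 1 to 2 point effect are illustrative assumptions, and so are the other values tabulated. Under them the within-arm understatement is 0.3 to 0.6 points (0.13 to 1.00 over the wider range), and a 10 v 5 split moves the contrast by roughly 0.2 to 0.5 standard errors.

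A reader might set that 0.2 to 0.4 point shift against the 1.8 in section 2.5 and report a large fraction of the planned effect. That comparison does not hold: 1.8 enters a paired-means calculation and is not a planned difference between the arms. The sample size does not change on this point.

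**What to change.** - **Professional treatment.** Add to 2.4.2 an exclusion for professional desensitizing treatment of the study teeth (varnish, oxalate, adhesive or resin coat, laser) in the last six months. This reuses the plan's existing window.
- **Dentifrice.** Add a look-back before Day 0 for desensitizing dentifrices. The documents give no basis for a particular length, so the investigators should set and justify it.
- **Fit with inclusion criterion 6.** State whether fluoride pastes count as desensitizing for this purpose. Section 1.1 lists sodium and stannous fluoride as tubule-plugging agents, and criterion 6 recruits fluoride-paste users. A rule that covered only non-fluoride pastes would miss the most foreseeable exposure.
- **Check and report.** Confirm both rules from the dental-treatment and hygiene history already taken, and report prior use by arm with the baseline data.

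The cost is a few lines of text and no new data collection. The downside is that some recent users are turned away or deferred, within a study of six months.

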In this six month In- Vivo single blinded Randomized Clinical Study, a total number of 50 patients with complain of dentine hypersensitivity will be selected in two groups after taking consent. Group A and B will receive Propolis and Dentine Bonding Agent respectively by a trained operator. Recordings of Dentin Hypersensitivity will be obtained at Day 0, before and after the application of experimental agents, and also on Day 7, 15 and 30 by the Researcher. Response will be measured by Visual Analog Scale and Schiff Cold Air Sensitivity Scale. SPSS v.20 will used to analyze the data with level of significance set at $p < 0.05$. Friedman test will be applied to see the comparison within groups and Wilcoxon Signed Rank test will be used for Pairwise comparison. Mann Whitney U-Test will be applied for comparison between groups.

Key Words: Dentin Hypersensitivity, Propolis, Dentine Bonding Agent, Visual Analog Scale (VAS), Randomized Clinical Trail, Schiff Cold Air Sensitivity Scale

CHAPTER 1: INTRODUCTION

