APPENDIX-II

[figure not shown]
Date: _____ Form no: _____ Envelop: _____

Patients Name: _____ Age: _____ Sex: _____

Address: _____

Contact No. : _____ Occupation: _____

VAS

Schiff Cold Air Sensitivity Scale

0 = Subject does not respond to air stimulus

1 = Subject responds to air stimulus but does not request discontinuation of stimulus

2 = Subject responds to air stimulus and requests discontinuation or moves from stimulus

3 = Subject responds to air stimulus, considers stimulus to be painful and requests discontinuation of stimulus

	VAS	SCASS
Day 0 (Before Application)		
Day 0(Immediately after application)		
Day 7		
Day 15		
Day 30

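### Section 2.8.2 leaves the within-group Wilcoxon pairs unnamed and unadjusted; if all pairs are tested, a false post-application change appears in about 20% per arm and scale

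*Combined protocol and SAP*

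**What the plan says.** Section 2.8.2 is the whole analysis plan. It sets the significance level at p < 0.05 and describes the within-group analysis in two sentences: "to see the comparison within groups, Friedman test will be applied", then "For Pairwise comparison, Wilcoxon Signed Ranked Test will be used". Mann-Whitney is reserved for the comparison between groups. The Methods part of the abstract says the same: "Friedman test will be applied to see the comparison within groups and Wilcoxon Signed Rank test will be used for Pairwise comparison".

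Neither place lists the pairs, names a multiplicity adjustment, or makes a significant Friedman result a condition for the Wilcoxon tests.

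The data collection form (headed Appendix II) has five rows. The first is "Day 0 (Before Application)" and the second is "Day 0(Immediately after application)"; Days 7, 15 and 30 follow. Section 2.8.1 lists the sessions as an independent variable and both scales as dependent variables. The abstract confirms the two scales: "Response will be measured by Visual Analog Scale and Schiff Cold Air Sensitivity Scale". Neither is named as primary.

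**The concern.** After a Friedman test over five sessions, an unqualified pairwise step is ordinarily read as all pairs, each judged at 0.05. Many readers would expect the Friedman test to limit the error. It does so only when all five readings are equal. The pre-application score is one of the five, and section 1.2 expects both agents to reduce sensitivity. A real fall after application is therefore enough to make Friedman significant, whatever happens afterwards. The comparisons among the immediate, Day 7, Day 15 and Day 30 readings are then tested with no error control.

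Those comparisons are the ones that would support a statement that an agent's effect builds up, holds or wears off within its own arm. At stake is the chance of reporting such a change when nothing changed after application.

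**Working it through.** The plan states no family-wise error rate, so there is no figure of its own to reproduce on this point. Its one computed figure, 5 patients per group in section 2.5, does reproduce: a paired t-test with difference 1.8, SD 0.42 and two-sided alpha 0.01 has power 0.893 at n = 4 and 0.9955 at n = 5. That figure does not bear on what follows.

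**Inputs from the documents.** Five readings (abstract, data form); two scales (abstract, 2.8.1); two arms of 25 (2.5); 0.05 per test with no adjustment named (2.8.2).

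**Inputs assumed.** SD 2 points; pre-application mean 6; within-patient correlation 0.5 to 0.8 between any two readings, or first-order autoregressive at 0.7; scores continuous, 0-10 integer, or four-grade. A second set of runs used correlation 0.3 to 0.8 on a bounded 0-10 scale. The documents give none of these values.

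**1. Count.**
- All pairs: C(5,2) = 5 × 4 / 2 = 10 per arm and scale; 10 × 2 × 2 = 40 in total.
- Post-application pairs only: C(4,2) = 4 × 3 / 2 = 6 per arm and scale.
- Comparisons with the pre-application score only: 4 per arm and scale; 4 × 2 × 2 = 16 in total.

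**2. Does Friedman protect the six pairs?** With a fall of 1.8 points or more, the five-reading Friedman test rejected in 97-100% of runs. In the second set (falls of 1.8 and 4 points) it rejected in 92-100%, and 90-100% covers all the runs made. In the first set, the chance of a significant Friedman result together with at least one false post-application difference equalled the chance without any gate to within 0.001. With no fall at all, the gate does hold the error at about 4-5%, but that is not the situation the protocol expects.

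**3. Error among the post-application readings.** For k equal means, an unadjusted pairwise rule gives at least one false difference when the range of k standard normals exceeds 1.96 × √2 = 2.77.
- k = 4: 0.203.
- k = 3: 0.122.
- k = 2: 0.050.

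Six independent tests would give 1 − 0.95^6 = 0.265; the shared readings bring this down to 0.203. Simulation with 25 per arm gave 18.7-21.6% on VAS-type scores and 17.9-21.8% on Schiff-type scores with four equal readings, and 12.6% with three.

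**4. Floor.** With an underlying fall of 6 points the rate was still 20.0-21.8% on VAS and 16.6-19.2% on Schiff. With a fall of 8 points, so that nearly all later scores are zero, it was 8.3-10.2% on VAS and at most 0.4% on Schiff.

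**5. Effect of adjustment.** When the four comparisons with the pre-application score are truly significant, Holm over ten pairs tests the smallest remaining p-value at 0.05 / 6 = 0.0083. The error over the six is then bounded by 6 × 0.0083 = 0.05, and simulation gave at most 0.04. A fixed 0.05 / 10 = 0.005 per pair is bounded by 6 × 0.005 = 0.03, and simulation gave about 1-3%.

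**The case against.** The strongest reply is that the set of tests is inferred from silence. Section 2.8.2 does not say all pairs. If the investigators meant only each later reading against the pre-application score, the six post-application comparisons are never run and the 20% does not arise. This stands as a condition on the figure. It does not remove the gap, because the text permits either reading.

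Second, the objective (1.5) and null hypothesis (1.6) ask which agent is more effective. A reader might infer that the trial's main conclusion carries a 20% false-positive risk. The documents do not support that: the question is answered by the Mann-Whitney comparison, which this point does not touch. The rationale (1.3) does mention long-term success, but as a choice between the two agents. No section commits to a within-arm claim of build-up or relapse.

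Third, the four post-application readings may not share one distribution. Section 2.7 has the response recorded on the next day for patients treated under local anaesthesia, whereas the form labels that row as immediate. The two passages need to be reconciled. If that reading truly differs from the later three, the rate is about 12%, so this also stands.

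A reader might also pool the error over arms and scales and quote a much larger figure. That would need a correlation between VAS and Schiff that the documents do not give, and it is not the family that an adjustment within arm and scale controls. No pooled figure is offered here.

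**Conclusion.** The point holds in conditional form. The plan names neither the pairs nor an adjustment, and Friedman over all five readings cannot protect the post-application comparisons once scores fall from the pre-application level. The chance of at least one false post-application change is about 20% per arm and scale, on two assumptions: all ten pairs are tested, and the four post-application readings have the same distribution. The figure hardly depends on the assumed SD or correlation away from the floor. The defect is confined to secondary within-group statements on onset and durability. It is worth correcting because the correction is cheap, not because it threatens the comparison between agents.

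**What to change.** In section 2.8.2, state which pairs will be tested within each arm and scale, and apply Holm across them. A shorter list is an acceptable alternative, for example the four comparisons with the pre-application score plus one durability contrast fixed in advance. The documents do not single out any pair of visits for durability, so the investigators should choose that contrast. Once the four baseline comparisons have rejected, Holm tests that single contrast at 0.05, which is adequate because only one such comparison remains. If a fixed threshold is preferred with all ten pairs, use 0.005 per pair.

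The change takes about two sentences, repeated in the abstract. The cost is somewhat less power for small changes between follow-up visits. A large fall from the pre-application score is not at risk: with the five-contrast list and a 4-point fall (2 SD), all four baseline comparisons stayed significant in every simulated trial.

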1.2 Literature Review

The properties of ideal desensitizing agent are that they should not irritate the pulp or cause discomfort on application or later on, easily applicable, effective long lastingly and it should not stained the teeth, as described by Grossman ²¹. Such treatment has not been discovered so far.

There is no Standard treatment till date for Dentine Hypersensitivity and this study aims to find one. Adhesive restoration materials and dentinal adhesives are considered dentinal tubule sealers and with the ability of sealing open dentinal tubules, it is used in the treatment of Dentin Hypersensitivity ²⁰. Reduction in Dentin Hypersensitivity with the application and penetration of resins for occlusion of dentinal tubules was suggested by Dayton et al and Nordenvell & Brannstorm ^{22, 23}. Various studies found the significant effect of Dentine Bonding Agent in the reduction of Dentin Hypersensitivity²⁴⁻²⁷. In a study conducted in Thailand, in 2008 by Tasanee Tengrungsun et al reported a significant reduction of Dentin Hypersensitivity by Dentine Bonding Agent and it was also superior to other experimental agent i.e. GaAIAs laser ²⁷. Prati C. et al reported a significantly decrease in Dentin Hypersensitivity with respect to the baseline values just after 10 minutes by Dentine Bonding Agent²⁴. Other studies also found a significant relief in the symptoms of Dentin Hypersensitivity when treated with Dentine Bonding Agent ²⁵, ²⁶. Duran et al in randomized split mouth study design concluded that Dentine Bonding Agents

significantly reduce the symptoms of Dentin Hypersensitivity and will be used in the treatment of Dentin Hypersensitivity ²⁸.

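### Section 2.8.2 tests change over sessions only within each arm, by unadjusted pairwise tests, so a claim that the two agents differ in their course over Days 7 to 30 has no named test

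*Combined protocol and SAP*

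**What the plan says.** Section 2.8.1 lists sessions and groups as the independent variables, and VAS and the Schiff scale as the dependent ones. Section 2.7 sets assessments on Day 0 before and after application, and "also on day of re-assessment at 7th, 15th and 30th day", so there are five per patient.

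Section 2.8.2 names three tests:

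- Within arms: "to see the comparison within groups, Friedman test will be applied".
- Pairs: "For Pairwise comparison, Wilcoxon Signed Ranked Test will be used".
- Between arms: "For between groups comparison, Mann- Whitney U- Test will be applied".

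The abstract gives the same scheme: "Friedman test will be applied to see the comparison within groups and Wilcoxon Signed Rank test will be used for Pairwise comparison". Significance is set at 5%. Neither place says which session pairs are tested, whether the pairwise p-values are adjusted, or at which session and on what quantity (score or change) Mann-Whitney is run.

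On purpose, section 1.5 asks which agent is more effective. Section 1.3 adds that the study should indicate the better of the two options for long-term success.

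**The concern.** The signed-rank test needs paired data. The arms contain different patients, so it can compare sessions only inside one arm. Every named test of change over time is therefore a within-arm test, although sessions and groups are both declared factors. If the thesis says that one agent holds its effect better over Days 7 to 30, the output closest to hand will be a significant change in one arm and a non-significant change in the other. That pattern is not a comparison of the two agents.

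A second problem sits inside each arm. If the Friedman test is meant to guard the pairwise tests, it cannot do so here. The fall from the pre-application score alone will make it reject, and the pairs are then tested at 5% each.

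**Working it through.** The plan prints no figure on this point, so there is none to reproduce.

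**Inputs from the documents.** Five assessments, two arms, two scales, 25 patients per arm (section 2.5), level 0.05.

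**Assumptions.** Two-sided tests and no dropout. For the simulations in steps 3 to 5: whole-number VAS, SD 2, between-visit correlation 0.5 to 0.7. The documents give no SD of within-patient change.

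**1. Number of tests.** Session pairs: 5 x 4 / 2 = 10, of which 4 x 3 / 2 = 6 are among post-application sessions. If every pair were tested: 10 x 2 arms x 2 scales = 40 Wilcoxon tests.

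**2. One-arm-only significance with identical agents.** If each arm has probability p of a significant result, exactly one arm is significant with probability 2p(1 - p):

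- no true change, p = 0.05: 2 x 0.05 x 0.95 = 9.5%
- p = 0.50: 50%, the maximum
- p = 0.80: 32%
- p = 0.99: 2%

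With p taken from the paired t-test (noncentral t, n = 25) as an approximation to Wilcoxon:

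| Change / SD of change | p | One arm only |
|---|---|---|
| 0.2 | 0.16 | 27% |
| 0.4 | 0.48 | 50% |
| 0.6 | 0.82 | 29% |
| 0.8 | 0.97 | 6% |
| 1.0 | 0.998 | 0.5% |

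Section 2.5 prints SDs of 2.93 and 3.35. If either were the SD of change, a 1.8-point change would give 27% and 39%. With that section's 0.42 the figure is about 0.

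**3. Simulation, identical arms, Day 7 against Day 30** (ranges over repeated sets of runs):

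| Common loss of effect, VAS points | Wilcoxon significant in one arm only |
|---|---|
| 0 | 7-10% |
| 0.5 to 1.0 | 28-47% |
| 1.5 | 1-14% |

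A Mann-Whitney test on each patient's Day 30 minus Day 7 stayed at 4-6% throughout.

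**4. Friedman as a gate.** With a fall at application and no change afterwards, Friedman rejected in 100% of runs. At least one of the six post-application pairs was falsely significant in 19-23% of arms on one scale, and in at least one of the two arms in 36-38% of trials. As a check at 20% per arm: 1 - 0.80 x 0.80 = 36%.

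**5. Level and change answer different questions.**

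- Arms 1.5 points apart from application onward, neither losing effect: Mann-Whitney on Day 30 scores was significant in 69-74% of runs, and the test of Day 30 minus Day 7 in 4-5%. A Day 30 difference is not by itself evidence of better persistence.
- Arm A stays at 5.5 while arm B goes from 2 to 3.5: the change test was significant in 63-86% of runs and favoured A, although B was still better at Day 30. Day 30 Mann-Whitney was significant in about 92% and pointed to B. Change alone is not a measure of durable benefit.

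**6. Why one contrast.** Testing all ten change contrasts between identical arms, unadjusted, gave at least one false positive in 29-31% of trials. This came from a separate simulation with other assumed means and SDs.

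**The case against.** The strongest reply is that the plan does compare the randomised arms. The Mann-Whitney sentence directly follows the pairwise one. Run at a post-treatment session, that test holds about 5% error and bears directly on early and later relief. This stands. A reader might infer that every claim about speed or duration would have to rest on within-arm p-values, or that the arms have no valid comparison at all. The documents do not support either. What is missing is a stated session and quantity for Mann-Whitney, and any named between-arm test of change.

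Second, no section says that within-arm p-values will be compared across arms. That is correct. The percentages in steps 2 and 3 describe a misreading that the plan leaves open, not one that it announces. They also depend on the contrast: large falls from Day 0 give almost none of it, and modest changes between follow-up visits give the most.

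Third, a reader might infer that the repeated visits exist to compare onset or persistence. No section says so. Speed of onset is not an objective, and "effective long lastingly" in section 1.2 describes an ideal desensitising agent, not a trial aim. Section 1.3 does raise long-term success, and a between-arm comparison at Day 30, the last visit, addresses that.

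Fourth, which Wilcoxon pairs will be run is not stated, so six or ten is a possibility and not a plan. That is why the false-change figure is conditional on all six being tested.

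**Conclusion.** The point holds as a gap in the analysis section that should be closed. It does not undermine the main efficacy comparison.

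- Which agent gives the lower score at a visit can be answered by Mann-Whitney once its session and quantity are stated.
- Whether the agents' effects change differently over Days 7 to 30 has no named test. The 9.5% figure with no true change and the 50% ceiling follow from the formula for a test at exactly 5%. The values between them rest on the assumed SD, correlation and size of change.
- Within an arm, about 20% per scale would show at least one false change if all six post-application pairs were tested on a flat course. Friedman gives no protection against this.

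**What to change.** In section 2.8.2:

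1. Keep the between-arm comparison at Day 30 as the efficacy and long-term result. Name its scale and quantity, preferably change from the Day 0 pre-application score or a comparison adjusted for it.
2. Add one pre-specified between-arm test of time course: either a Group x Session term in a repeated-measures model on VAS, or Mann-Whitney on Day 30 minus Day 7. State that it is read only together with the Day 30 comparison and is not the sole basis for a durability claim.
3. Limit the Wilcoxon tests to the four contrasts with Day 0 before application, Holm-adjusted within each arm and scale. Label them descriptive, and state that their p-values are not compared across arms.

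The cost is wording and, for the Mann-Whitney option, one computed variable. No new data are needed. Fewer within-arm results will be called significant. The time-course test will also be modest in power: by normal approximation, 25 per arm give 80% power only for a difference of (1.96 + 0.84) x sqrt(2/25) = 0.79 SD of the change score. A non-significant result should therefore not be reported as equal persistence.
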